- (1) To determine if a relatively brief, focused intervention in reappraisal-by-distancing in bereaved spouses engages the targeted mechanisms. Hypotheses: Distancing training is expected to result in longitudinal reductions in self-reported negative affect, increases in RSA, and changes in neural activity in a priori ROI's above (i.e., reductions in amygdala activity, increases in DLPFC activity) that are greater than those for reinterpretation training.
- (2) To examine the impact of changes in the targeted mechanisms in changing health-relevant behavior. Hypotheses: Across time and participants, reductions in self-reported negative affect, increases in RSA, and changes in neural activity are expected to lead to reductions in depressive symptoms and grief rumination.
- (3) As an exploratory aim, to mechanistically relate intervention effects to behavior change as a function of changes in the targeted processes. Crucially, this aim will also include assessment of interactions with age and gender of the bereaved spouse and initial depression and grief severity.

Hypotheses: Distancing training will lead to reductions in grief rumination and depression that are mediated by changes in the targeted neurobiological and behavioral mechanisms.

Sample Size::

84 bereaved participants will be recruited (i.e., N=42 per each intervention cell) and randomly assigned to receive either Distancing Training or Reinterpretation Training.

Power Analyses:

Outcome: Self-reported negative affect

Sufficient power to assess self-reported negative affect outcomes will be achieved by recruiting 42 participants per training cell. This sample size estimate is based upon a power analysis using an approximate effect size ($d=.70$) previously reported for within and between-subjects behavioral analyses of longitudinal reappraisal training data¹. Power analyses using this approximate effect size indicate over 95% power ($\alpha=.05$) to detect within-group effects and 90% power ($\alpha=.05$) to detect between-group effects should be achieved with 36 participants per cell. Assuming all-cause attrition of 15% (which reflects a liberal upper bound given past participant attrition rates of approximately 10%), the proposed sample size should provide sufficient power to assess this outcome. Post-attrition, we expect to have analyzable complete data for approximately 36 participants per cell.

Outcome: Respiratory sinus arrhythmia (RSA)

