Data analysis will primarily use linear mixed models, incorporating fixed effects for Training Group (Distancing and Reinterpretation), Session (T1-T5), and Trial Type (for analyses involving the reappraisal task; Look Neutral, Look Negative, and Reappraise Negative), and their interactions, as well as a random effect consisting of an intercept for each participant. In each analysis, statistically significant and near-significant intercept variance reflects reliable differences between participants. We will examine additional models that incorporate and estimate random-effects slope variance across participants on the time effect (i.e., Session). Outcome variables will be repeated measures in self-reported negative affect, RSA⁵, and neural activity (Aim 1) and changes in health-relevant behavioral outcomes (e.g., depressive symptoms and grief rumination; Aims 2 and 3). In these analyses, gender, age, baseline depressive symptoms, expectedness of the loss, and current (non-excluded) medication use will be incorporated as covariates. Importantly, given that we anticipate enrolling an approximately equal number of men and women, we also anticipate having sufficient power to conduct exploratory analyses on the effect of gender (and age) on the hypothesized effects (all Aims). Further, Aim 3 will be investigated using multilevel mediation modeling^{6,7} involving training group assignment as the higher-level predictor (X); self-reported negative affect, RSA data, and neural activity as potential individual-level mediators (M); and health-relevant behavior (i.e., depressive symptoms and grief rumination) as individual-level outcome variables (Y). Note that this will model mediation as a time-dependent and experimental process, both of which help

to rule out alternative explanations. Other exploratory model paths will also be tested. Appropriate covariates indicated above will be incorporated in all mediation models.

Data and Safety Monitoring Plan:

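### The SAP anticipates sufficient power for gender and age moderation without any interaction calculation; for gender by training group, unadjusted power is about 31% two-sided or 43% one-sided at an assumed 0.70 SD difference

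*SAP*

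**What the plan says.** The SAP's Data Analysis section (All Outcomes) expects about equal numbers of men and women and, on that ground, states "we also anticipate having sufficient power to conduct exploratory analyses on the effect of gender (and age) on the hypothesized effects (all Aims". No effect size, alpha level or calculation accompanies the statement there, and the protocol does not mention these analyses.

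The effects in question are set out under Specific Aims. Aim 1 expects changes under distancing "that are greater than those for reinterpretation training", which is a contrast between training groups. Aim 2 is a pooled association, with depression and rumination scores as the outcomes: "Across time and participants, reductions in self-reported negative affect, increases in RSA, and changes in neural activity are expected to lead to reductions". Aim 3 is labelled exploratory, and "this aim will also include assessment of interactions with age and gender of the bereaved spouse", along with baseline severity measures.

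The Power Analyses section uses the same language of sufficient power for each of its four outcome groups. For negative affect it begins "Sufficient power to assess self-reported negative affect outcomes will be achieved by recruiting 42 participants per training cell". In each case the claim is tied to an effect size of d = .70, over 95% power for within-group effects, and 90% power "to detect between-group effects should be achieved with 36 participants per cell". Interactions are not covered.

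**The concern.** Gender balance makes a comparison of men with women efficient for a given sample size. It does not make that sample size large enough, and it has no bearing on age.

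An effect of gender on the Aim 1 contrast is a difference between two between-group differences. With the same 72 analyzable participants split into four cells instead of two, its standard error is twice that of the main contrast. A design sized for the main contrast therefore does not carry its power over to the interaction.

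Elsewhere in the SAP, sufficient power goes with figures of 90% or more, so a reader may give the phrase the same meaning here. The practical risk is that a null gender-by-group result is read as evidence that men and women respond alike, when the study could have missed a substantial difference.

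**Working it through.** **Inputs from the SAP.** 42 recruited per group and 15% attrition: 42 × 0.85 = 35.7, about 36 analyzable per group and 72 in all. Alpha = .05, sidedness not stated. d = .70 for within-group and between-group effects. Roughly equal numbers of men and women.

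**Assumptions made here.** The gender split is even within each group, so 36 / 2 = 18 per cell. Each participant contributes one change score, in SD units. There is no variance reduction unless stated. The SAP gives no size for the interaction, so a range is shown. Power is from the noncentral t distribution.

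**Step 1: the SAP's own between-group figure.** SE = √(2/36) = 0.236 SD; noncentrality = 0.70 / 0.236 = 2.97; 70 df.
- One-sided .05: 90.3%.
- Two-sided .05: 83.4%.

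In an unadjusted t test the stated 90% matches the one-sided figure. A two-sided test would also reach about 90% if covariates removed about 18% of the variance (SE = 0.236 × √0.82 = 0.213). Sidedness therefore cannot be settled from this figure, and both versions are carried forward.

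**Step 2: gender by training group.** SE = √(4/18) = 0.471 SD, twice 0.236; 72 − 4 = 68 df.

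| Assumed difference between men and women in the group effect | Two-sided | One-sided |
|---|---|---|
| 0.35 SD | 11% | 18% |
| 0.70 SD | 31% | 43% |
| 1.0 SD | 55% | 68% |
| 1.4 SD | 83% | 90% |

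The 0.70 SD row borrows the SAP's only effect size. It makes the gender difference as large as the whole planned group effect.

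**Step 3: detectable difference at 18 per cell.**

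| Condition | Two-sided | One-sided |
|---|---|---|
| 80% power, unadjusted | 1.34 SD | 1.18 SD |
| 90% power, unadjusted | 1.55 SD | 1.39 SD |
| 80% power, assumed 50% of variance removed (SE = 0.471 × √0.5 = 0.333) | 0.95 SD | 0.84 SD |

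**Step 4: sensitivity at 0.70 SD (two-sided / one-sided).**
- 18% of variance removed, as in Step 1: 37% / 49%.
- No attrition, 21 per cell, 80 df: 35% / 48%.
- No attrition and an assumed 50% of variance removed: 61% / 73%.
- 14 of one gender and 22 of the other in each group: 30% / 42%.
- Variance that must be removed to reach 80% at 18 per cell: about 73% / 65%. The documents give no correlations or variances from which to judge this.
- Analyzable participants needed for 80%, unadjusted: 4 × 65 = 260 / 4 × 51 = 204, against 72 expected.

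**Step 5: the pooled alternative.** Comparing change in all men with change in all women, 36 v 36 at d = .70, is the same calculation as Step 1: 83% two-sided, 90% one-sided, unadjusted. It does not test whether gender alters the group effect.

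**The case against.** The strongest reply is that the sentence is hedged and can be read more kindly. It speaks of anticipating power, it calls the analyses exploratory, and it gives no number that could be contradicted. Aim 2 is framed across all participants, and a pooled comparison of men with women does reach 83% / 90% at d = .70. That stands for the pooled reading, but the sentence covers all Aims. Aim 1 is a between-group hypothesis and Aim 3 names interactions with gender, so the pooled reading cannot carry the whole claim.

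A second reply is that 0.70 SD was never proposed as an interaction size. That is correct, which is why a range and detectable differences are given. The absence of a calculation does not depend on it.

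Third, the SAP plans mixed models with covariates, so unadjusted figures may understate power. This also stands in part. Two stronger readings fail because of it. A reader might infer that the SAP must have used one-sided tests; modest variance reduction explains the 90% equally well. A reader might also infer that the claim can hold only if men and women differ by 1.2 to 1.3 SD; that applies to an unadjusted analysis at 80% power, and the threshold falls below 1 SD if half the variance is removed. Neither correction brings power at 0.70 SD to 80%.

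Finally, it is tempting to call the statement wrong for age and for every Aim. The documents do not support that: power for age depends on a slope they do not give, and moderation in Aims 2 and 3 depends on associations and variances they do not give.

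**Conclusion.** The power claim has no stated support beyond gender balance. For gender moderation of the Aim 1 group effect, the design does not deliver power of the kind the SAP reports elsewhere unless the difference is very large. Unadjusted, power at an assumed 0.70 SD is 31% two-sided or 43% one-sided, and about 37% / 49% if enough variance is removed to make the SAP's own 90% two-sided.

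These figures rest on about 18 analyzable participants per cell, an even gender split within groups and one change score per person. For age, and for moderation in Aims 2 and 3, the finding is only that no calculation supports the claim.

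Severity is minor. The analyses are exploratory, and the sample size, endpoints and models are unaffected.

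**What to change.** Amend the one sentence in the SAP's Data Analysis section.

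- Either withdraw the power claim for gender and age moderation of the training-group effect, or replace it for gender with the detectable difference. For example: with about 18 analyzable participants per gender-by-group cell and no variance reduction, 80% power is available for a difference of about 1.3 SD (two-sided .05) or about 1.2 SD (one-sided .05) between men and women in the training-group effect. Keep only the sidedness the SAP adopts, and state it.
- Make no power claim for age, or for moderation in Aims 2 and 3, unless a calculation and its assumptions are given.
- If a pooled comparison of change in men and women is what is meant, say so and limit the claim to that: 83% two-sided or 90% one-sided at d = .70, 36 v 36, unadjusted.

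The only cost is a less favourable power statement.
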